Use of SU-VEID™ As An Adjunct to Vein  
Visualization Technology to Improve Peripheral  
Venous Access Success in Children

NCT05204082

September 15, 2021

[figure not shown]
**Use of SU-VEID as an adjunct to vein visualization technology to improve peripheral venous access success in difficult venous access patients**

[figure not shown]
Title	Use of SU-VEID as an adjunct to vein visualization technology to improve peripheral venous access success in children
Study Number	1.0
Study Objectives	Intravenous access is often technically difficult in children because of the small diameter, inability to feel or see the veins. We propose to determine if use of the SU-VEID™ in children facilitates an increase success rate of peripheral intravenous starts, in comparison to conventional vein entry techniques.
Study Device	SU-VEID Single Use Vein Entry Indicator Device.  Electronic pressure sensing device, integrated to a conventional needle catheter, and which indicates continuously during intravenous cannulation: whether the tip of the needle is inside or outside of a vein, to assist a clinician in intravenous cannulation.
Indication for Use	The SU-VEID is used to indicate the location of the vein (in relation to a tip of a needle): including indication of vein entry, vein double puncture (infiltration), vein re-entry and vein exit of an intravenous catheter system's needle.
Study Design	
1- General
 
 
a. SRNAs, CRNAs, and Physicians in the anesthesiology department who normally performs IV Starts as part of patient care may participate.
 
b. Study type: Prospective, Randomized Controlled Trial
 
 
2- Clinician Training
 
Each participating clinician will watch a training video and practice on a phantom to gain proficiency with the SU-VEID device prior to study participation.
 
3- The trial
 
 
- The potential intravenous catheter inserter will assess the difficulty of the IV start preoperatively
 
- Pre-surgical subjects requiring an IV without adequate visually visible veins on the arms will be considered difficult venous access and approached for consent.
 
- Subjects who are consented/ assent will be assigned a study number and randomized to either standard IV insertion or with SU-VEID by the research assistant
 
- The clinician will perform procedures with or without SU-VEID, according to the randomization scheme. To allow analysis across all clinicians, an individual clinician's participation will be limited to no more than 50% above/below the number of subjects that would occur if the subjects were distributed equally
 
 
4- A minimum of 200 subjects per control group and 200 subjects for the Study group.
 
 
- Subjects will be stratified to 200 (100 control, 100 SU-VEID) total using near infra-red vein (NIR) visualization and 200 (100 control, 100 SU-VEID) total using ultrasound (US) vein visualization. Targeting type I/II error rates of 0.05 and 0.2, respectively, this sample size would detect improvement of first pass success from 50% to 66%.
 

Study Groups	Pediatric patients in surgical pre-op (0-18 years old), requiring an I.V. catheter for surgery who are difficult venous access.

Study Population	
Inclusion
 
 
-Patient age <math>\leq</math> 18 requiring an IV for surgery who is difficult venous access
 
-Written informed consent/ assent from the patient or legal guardian.
 
 
Exclusion
 
 
-Patient age <math>></math> 18
 
-placement of the IV will be done according to standard operating room procedures, which typically is after induction of general anesthesia by mask
 

Number of Subjects	A total of 400 difficult venous access patients will be stratified between using either 200 NIR or 200 US vein visualization technology to achieve venous access. Within each vein visualization device group, the patients will be randomized to either standard or using SU-VEID as an adjunct for IV catheter insertion. Please see above for sample size calculation.
Study Duration	6 months
# of Clinical Sites	1
Primary End Points	IV Start first-attempt success rate increases when using the SU-VEID Device in comparison to the conventional procedure.
Secondary End Point	
 
1- Success rate of IV access within two sticks when using NIR technology.
 
2- Success rate of IV access within two sticks when using US technology.
 
3- Total procedural time required to achieve successful cannulation in comparison to conventional IV Start procedure.
 

Statistical Analysis	Paired T-test (Each clinician conducts procedures with and without the device), Chi-Squared (Measuring differences in vein difficulty pre-assessment versus control and study group success rate),
Study Sponsor	Angie Technologies Ltd.

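### The stated 80% power for 50% versus 66% matches neither sample size in the plan: power is about 90% at 200 per arm and about 63% at 100 per arm

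*Combined protocol and SAP*

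**What the plan says.** The synopsis of the combined protocol and SAP gives two sizes in Study Design, item 4. The first is the overall size: "A minimum of 200 subjects per control group and 200 subjects for the Study group". The second is a split by modality: "Subjects will be stratified to 200 (100 control, 100 SU-VEID) total using near infra-red vein (NIR) visualization", with the same numbers for ultrasound. The power statement follows directly after the split: "Targeting type I/II error rates of 0.05 and 0.2, respectively, this sample size would detect improvement of first pass success from 50% to 66" per cent.

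The Number of Subjects row repeats the total ("A total of 400 difficult venous access patients will be stratified between using either 200 NIR or 200 US vein visualization technology") and gives no calculation of its own: "Please see above for sample size calculation".

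The primary endpoint is not split by modality: "IV Start first-attempt success rate increases when using the SU-VEID Device in comparison to the conventional procedure". The modality-specific endpoints are secondary and concern success within two sticks, not at the first attempt.

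The Statistical Analysis row lists first a "Paired T-test (Each clinician conducts procedures with and without the device") and then a chi-squared test relating pre-assessed vein difficulty to success. The documents give no sidedness, no number of clinicians, and no allowance for loss, clustering or multiplicity.

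**The concern.** A power statement ties together a size, a test, two error rates and a detectable difference. Here the size is ambiguous and the test is unnamed, and the remaining figures do not agree with either size in the plan.

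The two readings put the true power on opposite sides of 80%. If the 400 children are analysed together, the sentence understates what the trial can do. If it was meant to assure the sponsor that each modality can stand alone, it overstates it: a true 16-point gain would be missed about 37% of the time rather than 20%. Nothing else in the documents justifies enrolling 400 children, so a reader cannot tell what the trial is powered for.

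**Working it through.** **Inputs.** From Study Design, item 4: p1 = 0.50, p2 = 0.66, α = 0.05, β = 0.2, and n = 200 or n = 100 per arm, allocated 1:1. Assumed, because not stated: independent proportions and a two-sided test. One-sided results are also shown.

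**Components.** The mean rate is p̄ = 0.58.
- √[2p̄(1−p̄)] = √0.4872 = 0.6980
- √[p1(1−p1) + p2(1−p2)] = √(0.25 + 0.2244) = 0.6888

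**Attempt to reproduce the plan's figure: size needed for 80% power.**

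n = (1.960 × 0.6980 + 0.8416 × 0.6888)² / 0.16² = (1.3681 + 0.5797)² / 0.0256 = 148.2, so 149 per arm (161 with continuity correction; 117 if one-sided). None of these is 200 or 100.

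**Power at each size.** Power = Φ{[0.16 − z × 0.6980/√n] / (0.6888/√n)}

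- n = 200, two-sided: (0.16 − 0.0967)/0.0487 = 1.299, power 0.903
- n = 100, two-sided: (0.16 − 0.1368)/0.0689 = 0.337, power 0.632

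| Per arm | Two-sided power | One-sided power | Exact chi-squared, two-sided | Exact continuity-corrected, two-sided | Rate detectable from 50% at 80% power, two-sided |
|---|---|---|---|---|---|
| 200 | 0.903 | 0.947 | 0.901 | 0.882 | 63.8% |
| 100 | 0.632 | 0.744 | 0.643 | 0.588 | 69.3% |

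Unpooled-variance, arcsine, Fisher and McNemar (independent pairs) versions were also tried. At α = 0.05, no version comes within 2 points of 80% power at either size.

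**Unwritten allowances that would lead to about 200 per arm.**
- 25% loss: 149/0.75 = 199. (150 remaining per arm give power 0.805.)
- A clustering design effect of about 1.34: 200/149 = 1.34.
- α = 0.05/3: 198 per arm needed; power 0.805 at 200.
- α = 0.025 with continuity correction: 192 per arm needed; power 0.819 at 200.

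The documents mention none of them, and the last two contradict the stated 0.05.

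**The listed clinician-paired t-test (illustration only).** Assume equal caseloads, 200 per arm in total, and k clinicians. Each clinician's difference then has variance 0.4744/(200/k) + τ², where τ is the between-clinician SD of the device effect. The documents give neither k nor τ.

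| k | Power, τ = 0 | Power, τ = 10 points |
|---|---|---|
| 10 | 0.83 | 0.69 |
| 20 | 0.88 | 0.81 |
| 40 | 0.89 | 0.86 |

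**The case against.** The strongest reply is that on the natural reading the sentence is safe. The primary endpoint pools the modalities, the plan sets 200 per arm as a minimum, and a trial that targets a type II error of 0.2 and achieves about 0.10 has met its target. No first-attempt comparison within a modality is listed as an endpoint, so the 63% figure belongs to a comparison the plan does not formally make. This stands as far as consequences go: the primary comparison is not underpowered on these inputs. It does not make the figures agree. The sentence gives specific error rates and a specific detectable rate for its size, and it sits directly after the 100 + 100 split, so the modality reading cannot be ruled out.

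A second reply is that testing the sentence against independent proportions is the reviewer's choice. Under the listed paired t-test, power near 80% at 200 per arm is attainable, for example 0.81 with 20 clinicians and a 10-point between-clinician SD. Clustering by clinician is also a plausible reason for a larger size, since Study Design limits each clinician's caseload. Both points are fair, but they rest on quantities the documents do not contain. They show how the figure might have arisen, not that it follows from what is written.

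**Conclusion.** The concern holds. With the stated rates and α = 0.05, a type II error of 0.2 is reproduced at neither 200 nor 100 per arm, one-sided or two-sided. The two-sided values are about 0.10 at 200 per arm and about 0.37 at 100 per arm.

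Under the pooled reading, which fits the primary endpoint, the error is conservative: 80% power applies to a gain of about 14 points rather than 16, and no primary conclusion is endangered. The shortfall to 63% applies only if each modality was meant to be powered for first-attempt success.

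These figures rest on independent proportions with no loss or clustering. They do not carry over to the clinician-paired t-test. The point should be fixed because it concerns the only justification for the size of the trial, but it does not invalidate the design.

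**What to change.** Replace the power sentence in Study Design, item 4, with one that names the comparison, test and sidedness and gives matching figures. For example:

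*For a two-sided 0.05 comparison of two independent proportions, 200 per arm with modalities combined gives about 90% power for 50% versus 66%, or 80% power for 50% versus 63.8%. Within a modality, 100 per arm gives about 63% power for 50% versus 66%, or 80% power for 50% versus 69.3%.*

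The sponsor should also say which size the existing figure referred to, and state any allowance for loss, clustering or multiplicity that was used. If the clinician-paired t-test is the primary test, its power needs a separate statement with the assumed number of clinicians and the assumed variation of the device effect between them.

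The cost is a few sentences, with no change in enrolment. The pooled figure becomes more favourable. The modality-level figure, if one was intended, becomes less favourable.

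### Does the second Exclusion bullet, which describes how the IV is placed, leave it unclear whether children cannulated after induction are eligible?

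*Combined protocol and SAP*

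**What the plan says.** All the relevant text is in the synopsis table.

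- **Study Population, Inclusion:** patients aged 18 or under, "requiring an IV for surgery who is difficult venous access", with written consent or assent. Nothing is said about timing relative to induction.
- **Study Population, Exclusion:** two bullets. The first is age over 18. The second is "placement of the IV will be done according to standard operating room procedures, which typically is after induction of general anesthesia by mask".
- **Study Groups:** "Pediatric patients in surgical pre-op (0-18 years old), requiring an I.V. catheter for surgery who are difficult venous access".
- **Study Design, item 3 (The trial):** "The potential intravenous catheter inserter will assess the difficulty of the IV start preoperatively". Then "Pre-surgical subjects requiring an IV without adequate visually visible veins on the arms will be considered difficult venous access and approached for consent". Those who agree are "randomized to either standard IV insertion or with SU-VEID by the research assistant".
- **Number of Subjects:** within each visualization group, "the patients will be randomized to either standard or using SU-VEID as an adjunct for IV catheter insertion".
- **Study Design, item 1 (General):** "SRNAs, CRNAs, and Physicians in the anesthesiology department who normally performs IV Starts as part of patient care may participate".

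Induction of anesthesia is mentioned only in the second Exclusion bullet.

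**The concern.** The first Exclusion bullet merely mirrors the inclusion age limit, so it removes nobody who already qualifies. That leaves the second bullet as the only one that could turn away an otherwise eligible child, and it names no patient characteristic to screen on.

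Taken at face value under its heading, it would bar children whose IV is placed after mask induction, which the sentence itself describes as typical. That would sit badly with an inclusion rule covering any difficult-access child who needs an IV for surgery, and with a control arm defined as standard insertion. The Study Groups row, which locates the patients in pre-op, could be read as supporting such an exclusion.

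What would be at stake is the definition of the population: whether the result applies to children cannulated before induction, after it, or both. Bias between arms is not at issue, because assignment follows eligibility and consent.

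**Working it through.** No arithmetic applies. The plan gives no figure on this point and no count of IVs placed before or after induction. The check is to try each reading of the bullet against the other rows.

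**Reading A: a true exclusion.**

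1. Grammar. The sentence is a future-tense statement about conduct. To make it a criterion, the reader must supply an opening such as *patients in whom*. So this reading is a reconstruction, not the literal text.
2. Inclusion row. It has no timing condition, so the exclusion would remove what the bullet itself calls the typical case from a population the inclusion row admits without reservation.
3. Control arm. Study Design item 3 and the Number of Subjects row both define the comparator as standard insertion. Reading A would exclude placement by standard operating room procedure while making standard insertion the comparator.
4. Study Groups row. It says where the patients are found. It is compatible with Reading A but does not say where or when the cannula goes in.

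Reading A therefore needs added words and creates two tensions (steps 2 and 3).

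**Reading B: a procedure note under the wrong heading.**

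1. Grammar. The sentence stands as written.
2. Inclusion row. There is no conflict. Children cannulated after induction are eligible, and since the bullet says only what is typical, other timings are not barred.
3. Control arm. There is no conflict. Standard insertion is what the sentence describes.
4. Study Groups row and trial steps. There is no conflict. Patients are found in pre-op, difficulty is judged and consent sought before surgery, and placement follows usual operating room practice.
5. Operators. Anesthesiology staff could place an IV before or after induction, so this row fits either reading and does not discriminate.

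Reading B needs no added words and creates no conflict.

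**Scale.** One of the two Exclusion bullets is affected. It does not follow that the setting of all 400 planned patients is undefined: the sentence is itself the plan's statement of setting, and only its heading is in doubt.

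**The case for a change.** The best case for a change is that Reading B, however natural, is an inference. No other text confirms it, and an eligibility rule should not oblige screening staff to disregard the heading it sits under. On Reading B the list also contains no exclusion that adds to the inclusion criteria. Timing could be a relevant descriptor, too: difficulty is judged before surgery from visible arm veins, the cannula typically goes in later, and the Clinical Background section says the blood-return cue depends on venous pressure and volume status. On that view the plan should settle the wording and, if both timings are eligible, record timing before randomization and describe success by arm within each.

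Some of this stands. The heading is wrong for the sentence, and the sponsor would do well to reconcile the two when the document is next edited. That the list then excludes nobody beyond the age limit is true but is not a fault; the inclusion criteria already define the population.

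The rest does not carry a change. The phrase locating patients in pre-op cannot count as evidence of pre-induction placement when the parallel wording about preoperative assessment and pre-surgical consent is accepted as silent on cannulation. Recording and reporting by timing is an optional extra: the plan does not make timing a stratification factor, an endpoint or an effect modifier, and no gain in bias, power or precision was shown.

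The bullet also begins in lower case, unlike its neighbors, which might point to a displaced fragment. That cannot be verified here, and the conclusion does not depend on it.

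**Conclusion.** The observation is accurate, but no change to the plan follows. A sentence about how the IV is placed is listed under Exclusion; the reading that needs no added words and conflicts with nothing else is that it is a misfiled procedure note. Relocating it would be a clerical correction, with no change to enrollment on that reading, to the randomized comparison or to the analysis.

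This rests on one assumption: that the sponsor did not mean to exclude children cannulated after induction. Every row is consistent with that, though none states it outright. If an exclusion was in fact intended, the passages would need to be reconciled and the criterion written out at patient level. How many children that would affect cannot be computed from the documents. Nothing here bears on how or when IVs should be placed.

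### Two-stick success is planned only separately within NIR and within US; an overall SU-VEID versus control comparison in all 400 children should be added and the contrast stated

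*Combined protocol and SAP*

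**What the plan says.** The Secondary End Point row of the synopsis lists three items. The first two are "Success rate of IV access within two sticks when using NIR technology" and "Success rate of IV access within two sticks when using US technology". The third is "Total procedural time required to achieve successful cannulation in comparison to conventional IV Start procedure". The Primary End Points row reads "IV Start first-attempt success rate increases when using the SU-VEID Device in comparison to the conventional procedure". The primary endpoint and the third secondary item therefore name the conventional procedure as comparator, and the two-stick items do not. The primary endpoint is also not split by technology.

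The Number of Subjects row gives the structure: "A total of 400 difficult venous access patients will be stratified between using either 200 NIR or 200 US vein visualization technology", and then "Within each vein visualization device group, the patients will be randomized to either standard or using SU-VEID as an adjunct for IV catheter insertion". The Study Design row gives 200 per arm overall and 100 per arm within each technology. Its sample-size statement concerns first-pass success only. The Statistical Analysis row names a paired t-test by clinician and a chi-squared test. It ties neither to two-stick success and does not say whether the technologies are combined.

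**The concern.** Two things are unsettled for two-stick success.

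- **The contrast is not written down.** Each item is a success rate within one technology, and no arm is named.
- **Once the contrast is supplied, it exists only in halves.** There would be one comparison of 100 v 100 in NIR and another in US, with no comparison of 200 v 200.

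The Benefit section claims fewer attempts with the device. First-attempt success bears on that directly. Two-stick success is the only planned endpoint that counts sticks beyond the first, since the third secondary item measures time. Splitting it gives up precision that the randomisation has already provided. It also invites two verdicts that can disagree by chance, which could be misread as the device working with one technology and not with the other. If the contrast and the pooling stay unstated, both can be chosen after the results are seen.

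**Working it through.** **Inputs from the documents.** There are 400 children: 200 NIR and 200 US, with 100 control and 100 SU-VEID in each, so 200 per arm overall. Alpha is 0.05, with sidedness not stated; I use two-sided. First-pass success is 50% v 66%.

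**The plan's own figure.** It concerns first-pass success, not two-stick success. With the pooled-variance normal approximation, 50% v 66% at 80% power needs 149 per arm two-sided (117 one-sided). The planned 200 per arm gives 90% power and 100 per arm gives 63%, so neither size reproduces the stated 80%. That is a separate matter; nothing below depends on it.

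**Loss of precision.** For given rates, the standard error of a difference is sqrt{[p1(1−p1) + p2(1−p2)]/n}. Moving from n = 200 to n = 100 per arm multiplies it by sqrt(200/100) = 1.41, whatever the rates, provided they are the same in both technologies.

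**Power.** The documents give no two-stick rates, so every rate here is an assumption. The formula is power = Φ{[d − 1.96·s0]/s1}, with d = p2 − p1, s0 = sqrt[2·p̄(1−p̄)/n], p̄ the mean of p1 and p2, and s1 the standard error above. Clustering by clinician is ignored, because the documents give no figure for it.

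*Case A.* Two independent sticks, each at the planned first-pass rate: 1 − (1 − 0.50)² = 0.750 and 1 − (1 − 0.66)² = 0.884. Then d = 0.134 and p̄ = 0.817.
- n = 100: s0 = 0.0547, s1 = 0.0539; (0.134 − 0.1072)/0.0539 = 0.50; power 0.69.
- n = 200: s0 = 0.0387, s1 = 0.0381; (0.134 − 0.0758)/0.0381 = 1.53; power 0.94.
- 95% CI half-width, 1.96·s1: 10.6 points at n = 100 and 7.5 at n = 200.

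*Case B.* A smaller effect, 75% v 85%.

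*Case C.* A lower control rate. The Clinical Benchmark section puts the average at three or more attempts in difficult-access patients. A mean of 3 under independent sticks implies 1/3 per stick, so two-stick success is 1 − (2/3)² = 55.6%. Adding the planned 16 points per stick gives 49.3% per stick, and 1 − (0.507)² = 74.3%.

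| Assumed control v SU-VEID | Power per technology (100 per arm) | Power overall (200 per arm) |
|---|---|---|
| A: 75% v 88.4% | 69% | 94% |
| B: 75% v 85% | 42% | 71% |
| C: 55.6% v 74.3% | 80% | 98% |

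One-sided, case A gives 80% and 97%.

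**Chance of discordant results, case A.** With the same true effect in both technologies and independent strata:
- both significant: 0.69² = 0.48
- exactly one significant: 2 × 0.69 × 0.31 = 0.43
- neither significant: 0.31² = 0.10

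**The case against.** **The contrast is not really in doubt.** The study objective is a comparison with conventional technique, and both arms are randomised within each technology. This stands. A reader might infer from the literal wording that each item is one rate with the arms mixed, and so says nothing about the device. The documents do not support that: nowhere do they say that the arms are combined, and the design makes the comparison available. The unstated contrast is missing detail and no more.

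**Results by technology are a legitimate question.** The Device Description ties the expected benefit to keeping the clinician's eyes on the ultrasound screen or the NIR field, so an effect specific to each technology is worth estimating. Secondary endpoints need not each have 80% power, and the plan claims none for them. This stands too, and is why both items should be kept.

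**The effect size is constructed.** The plan states a first-pass effect only. It does not say that a second stick succeeds as often as the first, or that SU-VEID is used on it. Independence between sticks is doubtful in children selected for difficult access. This stands, so the power figures are illustrations. A reader might also infer that a comparison by technology would probably miss the planned effect. That does not follow: the plan has no two-stick effect, and under case A each comparison detects the difference about 69% of the time.

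**The overall result can be computed later from the same data.** That is true, but unless it is prespecified it becomes a choice made after the results are known. The 1.41 ratio needs none of the assumed two-stick rates.

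**Conclusion.** The point holds as a cheap improvement. Two-stick success is listed only by technology, with no comparator named and no overall comparison, in a trial that randomises all 400 children between the same two arms. Each planned item uses 200 of the 400 and has a standard error about 1.41 times that of the overall comparison. The power gain is from 69% to 94%, 42% to 71%, or 80% to 98%, depending on the rates assumed, and in the first case there is about a 43% chance of one significant and one non-significant result from the same true effect. The size rests on assumed two-stick rates, a two-sided 0.05 test, a common effect in both technologies and no clustering by clinician. The primary endpoint and its conclusion are not affected.

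**What to change.** Add one secondary endpoint: the difference between SU-VEID and control in the proportion of children cannulated within two sticks, in all randomised children, stratified by NIR/US. Reword items 1 and 2 as the same SU-VEID versus control difference within NIR and within US, each with a confidence interval. Say that these are read alongside the overall estimate, and that a significant result in one technology only is not by itself evidence that the effect differs between them.

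The cost is wording and one more secondary analysis. No further children or data are needed. The trade-off is that the results by technology are no longer the only two-stick results and have to be interpreted together with the overall one.

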### **Benefit**

Subjects may benefit by having the IV catheterization procedure performed with less attempts, easier and quicker with the SU-VEID device, therefore less exposure to risks.

Further, SU-VEID does not interfere with the normal blood return into the flash chamber of the catheter so its use does not obstruct a clinician's normal cues of entry into the vein. What it does is identify the precise time of entry into the lumen even if the patient's volume status is low and blood refill into the catheter is slow. This should allow the clinician to reduce "back wall" injury of the vessel and hence increase success.

Terms:

SU-VEID	Disposable sterile vein entry indicator device, FDA approved.
Success	The cannula is placed inside a vein and secured.
Fail	The procedure stopped due to a failure or the cannula found to be placed outside a vein right after completing the procedure, or a short time later.
IN-State	The needle's tip or the cannula's tip are inside a vein.
Sound of success	Fast beeps (8 per second) indicating in-vein Success state.
Sound of operation	Slow beeps (1 per second) indicating out of vein state
Half Detach	A temporary state while pulling the needle from a cannula or sliding forward the cannula on the needle for about an inch, the clinician normally ceases the detachment for a moment and hold (to see the blood upward in cannula) while the needle is still partially inside the cannula.
Full Detach	A state, where the needle is fully pulled out from the cannula.
AT	Angie Technologies Ltd.
SPIV	Short Peripheral Intravenous
DVA/DIVA	Difficult Intravenous Access

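### Does the time-to-cannulation endpoint need a rule for children who are never cannulated?

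*Combined protocol and SAP*

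**What the plan says.** The Secondary End Point row of the synopsis table gives the third endpoint as "Total procedural time required to achieve successful cannulation in comparison to conventional IV Start procedure". The Terms table under Benefit defines success as "The cannula is placed inside a vein and secured". Its entry for failure begins "The procedure stopped due to a failure or the cannula found to be placed outside a vein right after completing the procedure" and extends to a cannula found misplaced a short time later.

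The Statistical Analysis row names two methods. One is "Paired T-test (Each clinician conducts procedures with and without the device", with no endpoint attached. The other is a chi-squared test, described as "Measuring differences in vein difficulty pre-assessment versus control and study group success rate", which is not a time analysis. The only limit on sticks anywhere is in the first two secondary endpoints, for example "Success rate of IV access within two sticks when using NIR technology".

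The plan does not state when the clock starts and stops, whether time runs on through further sticks or another inserter, or what value a child has if cannulation is never achieved. It also does not say that such children are left out.

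**The concern.** A time to success does not exist for a child without success, and the Terms table recognises procedures that stop because they failed. The only listed method suited to a continuous outcome is a t-test, which cannot use a child without a time. The path of least resistance is therefore a comparison among successes.

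That subset forms after randomisation, in a trial designed to show that the device changes success: the Study Design row plans for first-pass success rising from 50% to 66%. If the device also raises final success, it does so mainly in hard children, who take longest. Their long times then count in the device arm, while similar children drop out of the control arm. A true saving could be shrunk, hidden or reversed. The sponsor's own device would be the loser.

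**Working it through.** **Is there a figure to reproduce?** No. The plan states no time, no final success rate and no power for this endpoint. The only design inputs are first-pass success of 50% v 66% and 200 children per arm (Study Design row). Everything else below is assumed.

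**Step 1: direction, by hand.** Let half the children be easy (3 min) and half hard (10 min), with no device effect on any child's time. Let success be 95% in easy children in both arms, and 55% (control) v 82% (device) in hard children. Mean time among successes:

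- control: (0.95×3 + 0.55×10)/(0.95 + 0.55) = 8.35/1.50 = 5.6 min
- device: (0.95×3 + 0.82×10)/(0.95 + 0.82) = 11.05/1.77 = 6.2 min

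The device looks slower only because it succeeds in more hard children. The mechanism is real.

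**Step 2: size, one procedure per child.** Let difficulty be x ~ N(0,1), success probability s(x) = 1/(1 + exp(−(a − x))) with a set to give the stated rate, and time t(x) proportional to exp(0.4x) with mean 3.40 min. The mean among successes is E[t(x)s(x)]/E[s(x)]. There is no device effect on speed.

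| Children with a time, control v device | Mean among successes (min) | Apparent difference |
|---|---|---|
| 50% v 66% | 2.84 v 3.00 | +5.4% |
| 90% v 95% | 3.26 v 3.32 | +2.0% |
| 95% v 98% | 3.32 v 3.37 | +1.3% |
| 100% v 100% | equal | 0% |

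The first row uses first-pass rates as if they were final rates, so it is an extreme.

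**Step 3: size, repeated sticks.** Use the same model per stick, with first-pass success 50% v 66%, equal time per stick and at most K sticks. A child is cannulated with probability 1 − (1 − s(x))^K. Success on stick k takes k×t(x); a child never cannulated is charged K×t(x) in the all-children mean. K is an assumption throughout.

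| K | Finally cannulated | Without a time, of 200 | Difference, all children | Difference, successes only |
|---|---|---|---|---|
| 2 | 70.7% v 84.8% | 59 v 30 | −10.4% (5.38 v 4.82 min) | 0.0% (3.95 v 3.95 min) |
| 4 | 86.8% v 95.2% | 26 v 10 | −21.0% | −9.2% |
| 6 | 92.8% v 97.9% | 14 v 4 | −26.3% | −15.6% |
| 50 | nearly all | about 0 | −38.5% | −37.2% |

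At K = 2, with the success slope varied from 0.5 to 2 and the time slope from 0.2 to 0.8, the successes-only difference runs from −4.3% to +12.4%, against −8.7% to −10.6% in all children.

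**Step 4: do the documents point to the damaging case?** Three passages bear on this.

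- *Study Population row.* Every child enrolled needs a line for surgery. Further sticks after a failed one are the natural expectation, so most children should end with a time.
- *Terms table.* The failure entry describes a procedure. It fits a failed attempt followed by another stick as well as a child left without a line.
- *Clinical Benchmark.* It gives an average of at least three attempts in difficult-access patients. With attempts ending at two, the mean cannot exceed two. In the model it is 1 + 0.50 = 1.50 in control and 1 + 0.34 = 1.34 with the device. The case in which the saving vanishes is therefore hard to square with the protocol's own benchmark, and the two-stick limit belongs to other endpoints.

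With four or more sticks, both columns of the table favour the device.

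**The case for a change.** The case for a change is respectable. The gap is in the text, it is not a redaction, and the listed t-test invites a successes-only analysis. The need for a line does not prove that every child's time is captured, because the plan does not say whether the clock runs on when another inserter or technique takes over. In the repeated-stick model a successes-only mean still understates the saving by about 11 percentage points at six sticks (26.3 − 15.6 = 10.7), when only 14 v 4 of 200 lack a time. Ranking children never cannulated below the slowest success, in a Wilcoxon test stratified by visualisation method, would need no extra data beyond a failure flag.

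What stands is that the rule is unwritten, and that a successes-only comparison should be read cautiously if final failure proves common or unequal.

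The rest carries less weight. The all-children mean charges an abandoned sequence as though it ended in success, so it is not time to cannulation. The ranking would not estimate it either, and the 11 points are not what a new analysis would recover. The ranking also mixes success with speed, although success is already the primary endpoint and the first two secondary endpoints, so it could show a gain with no difference in speed. And it drops the pairing by clinician that the plan's t-test uses. A time-to-event analysis would be another reasonable choice. No single correction follows from the documents.

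**Conclusion.** No change to the plan follows. The endpoint is silent on children never cannulated, but the documents do not show that following it gives a wrong answer. If nearly all children are finally cannulated, which is plausible in children who need a line for surgery, the distortion with no true speed effect is about 1% to 2% under the assumed slopes, and it is nil if all are. Losing the saving altogether requires a stop at two sticks that the plan does not set. The distortion in these illustrations also runs against the device, so it is unlikely to create a false claim of benefit.

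This is a detail that analysts would ordinarily settle: count time over all sticks, report how many in each arm were never cannulated, and add an analysis of all randomised children if that number is not negligible. The primary endpoint is untouched. The conclusion rests on final failure being uncommon, which the documents make likely but do not state, and on illustrative times and slopes that do not come from them.
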